10.3. Statistical Analyses

All primary, secondary and exploratory outcomes will be collected for all participants, except that PK analyses will be performed only for participants randomized to phenserine.

Trial management and data management will be conducted by the University Hospital Stavanger Clinical Trials Unit and the trial statistics will be led by [name], King's College London.

Standard safety data (including all AEs, TEAEs, SAEs, important clinical laboratory findings, and AE-related discontinuations) will be summarized for each treatment arm and dose level.

Exosome biomarker values will be natural log transformed to avoid skewness. To assess the effect of phenserine on a given biomarker, a linear mixed-effects model will be used, with treatment groups (phenserine vs donepezil), time, baseline biomarker, and plate to plate variability in exosome concentration (determined by NanoSight) as fixed effects and participant identification treated as a random effect.

To demonstrate that dropout rates are Missing at Random (MAR), we will calculate the correlation between dropout indicators (e.g., whether a participant drops out) and key covariates, including treatment group, baseline characteristics, and other relevant random effect categories. Based on prior observations (liraglutide trial for example), we expect that the likelihood of dropout will largely be explained by observed factors, especially drug treatment status. A logistic regression model will be used, with the dropout indicator as the dependent variable and treatment status, baseline covariates, and any other relevant factors as independent variables. If the model explains a significant portion of the dropout pattern, this would support the MAR assumption. Sensitivity analyses will also be conducted to assess the robustness of this finding under alternative missingness mechanisms.

For clinical secondary and exploratory outcomes, change from baseline will be calculated at the final study assessment (mean, n, standard deviation, standard error, minimum and maximum scores).

The primary outcome is the difference between treatment groups in key proteins measured in neuronally derived exosomes. Based on the previous work of Goetzl et al(30,31) between group differences of 4.9 SD were achieved in these measures. Assuming a difference of half of this magnitude (2.45 sd), a sample size of 4 participants per arm would be needed to give 80% power to detect a difference between groups to the 0.05 level of significance. The additional participants receiving phenserine will provide valuable information for safety reporting.

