10.3.1. General Considerations

The statistical analysis plan for this study is designed to assess the efficacy, safety, and pharmacokinetic properties of phenserine compared to donepezil in participants with early or mild Alzheimer's Disease (AD). Analyses will be conducted on a modified intent-to-treat (mITT) population, which includes all randomized participants who receive at least one dose of study medication and have at least one post-baseline assessment. All statistical tests will be two-sided, with a significance level set at 0.05.

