2.4 Timing of Outcome Assessments

The timing of all outcome assessments is predefined in the study protocol and summarized in the Schedule of Activities (SoA) (Protocol Section 1.3, Table 1). Outcome measures are collected at screening, baseline, and at scheduled on-treatment and follow-up visits during the 8-week treatment period and safety follow-up.

For all clinically planned outcome measures, visits should occur within the predefined visit windows. Assessments performed outside the allowable visit window will be considered protocol deviations, unless otherwise justified and documented. Only assessments obtained within the protocol-specified windows will be used for primary and secondary analyses.

The target days and visit windows relevant for efficacy, pharmacodynamic, pharmacokinetic, and safety analyses are defined as follows:

Visit Label	Visit Window
Screening	Within 28 days prior to baseline
V1: Baseline / Randomization	Day 0
V2: Week 2	Day 14 ± 3 days
V3: Week 4	Day 28 ± 3 days
V4: Week 6	Day 42 ± 3 days
V5: Week 8 / End of Treatment	Day 56 ± 3 days
Safety Follow-up / EOS	Within 28 days after last dose

Assessments collected outside the visit window will not be included in the primary analysis but may be listed and summarized descriptively.

3 Study Design Overview

- Design: Open-label, randomized (6:2), parallel-group Phase 1b study
- Treatment Arms:
 - Phenserine (dose-escalation up to 10 mg TDS)
 - Donepezil (5–10 mg OD)
- Treatment Duration: 8 weeks
- Sample Size: n = 16 (Phen: n=12; Donepezil: n=4)

Given the exploratory nature and small sample size, all analyses will be descriptive, and estimation focused.

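### The protocol's dropout regression cannot support missing at random over missing not at random, and no specified sensitivity analysis tests the treatment contrast

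*Protocol*

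**What the plan says.** Protocol 10.3 states its aim as follows: "To demonstrate that dropout rates are Missing at Random (MAR), we will calculate the correlation between dropout indicators" and key covariates. It then names a logistic regression of the dropout indicator with "treatment status, baseline covariates, and any other relevant factors as independent variables". No post-baseline biomarker value is listed, although the last category is open. The protocol gives its expectation in advance: "we expect that the likelihood of dropout will largely be explained by observed factors, especially drug treatment status". The decision rule is: "If the model explains a significant portion of the dropout pattern, this would support the MAR assumption". The next sentence adds: "Sensitivity analyses will also be conducted to assess the robustness of this finding under alternative missingness mechanisms". No method is given for these analyses.

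SAP section 6 has no dropout model and makes no statement about MAR. It rules out imputation, uses observed data on a complete-case basis, describes missingness patterns and contains no missing-data sensitivity analysis. SAP 3.3 already tabulates reasons for withdrawal by arm. SAP section 11 lists no change from the protocol on this point and defers any deviation to the study report.

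**The concern.** MAR means that, given what was observed, dropout does not depend on the values that are missing. MNAR means that it still does. The regression has only observed variables on its right-hand side. Its null hypothesis is that dropout is unrelated to them. Rejecting that null speaks against MCAR and leaves MAR versus MNAR where it was.

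The likelihood-based mixed model for the exosome markers relies on missingness being ignorable. If the rule is applied as written, a study report could cite a significant dropout model as support for that assumption when it is no such thing. The promised sensitivity analyses are aimed at the robustness of the MAR finding, not at the treatment effect. So no specified analysis shows whether the phenserine-donepezil contrast would survive non-ignorable dropout. With four donepezil participants, one loss removes 1/4 = 25% of the comparator.

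**Working it through.** **Inputs.** Allocation is 12:4 (SAP section 3: "Sample Size: n = 16 (Phen: n=12; Donepezil: n=4"). For the test level, Protocol 10.3.1 says: "All statistical tests will be two-sided, with a significance level set at 0.05". The protocol does not define what portion counts as significant, so I take the overall likelihood-ratio (LR) test of the logistic model at 0.05. No planning dropout rate is given. The only discontinuation rates for a phenserine regimen and a control are 23.6% and 17.1%, from an earlier trial (Protocol 2.3.1). The mechanisms below are therefore assumptions.

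**The plan's own figure.** The MAR rule carries no number. The one figure for the primary contrast is 4 per arm for 80% power at 2.45 SD. The normal approximation is 2 × (1.96 + 0.84)² / 2.45² ≈ 2.6, so 3 per arm. Exact t-test power is 61.9% at 3 and 82.1% at 4 per arm, so the stated figure reproduces. At 12:4 with no loss it is 97.6%.

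**Step 1: why the rule cannot discriminate.** Let R be dropout, T arm, X the other observed predictors and Y the unseen outcome. The regression sees only P(R | T, X). Under MNAR, P(R | T, X) is the average of P(R | T, X, Y) over Y given T and X. A MAR mechanism with exactly that averaged probability gives the same joint distribution of R, T and X. The rule is then met equally often under both. Adding observed post-baseline values to X does not change the argument.

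**Step 2: simulation.** Baseline b is standard normal. Week 8 value y = 0.5b + √0.75 × noise, so y has SD 1. The true arm difference is 0. The dropout model contains arm and b. The contrast is the baseline-adjusted difference among those observed. There were 3,000 runs at N = 16 (12:4) and 200 at N = 1,600 (1,200:400). Expit is the inverse logit.

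| Assumed dropout mechanism | Dropout, phenserine / donepezil | Rule met, N = 16 | Rule met, N = 1,600 | Bias (SD), N = 16 / 1,600 |
|---|---|---|---|---|
| MCAR: 0.25 in both arms | 25% / 25% | 10.5% | 7% | 0.00 / 0.00 |
| MAR, arm only: 0.35 / 0.05 | 35% / 5% | 16% | 100% | -0.01 / 0.00 |
| MAR, arm and baseline: expit(-0.75 + 1.5b) / 0.05 | 37% / 5% | 58% | 100% | -0.02 / 0.00 |
| MNAR: expit(-0.75 + 1.5y) / 0.05 | 37% / 5% | 27% | 100% | -0.31 / -0.32 |
| MNAR, equal rates: expit(-1.35 + 1.5y) / expit(-1.35 - 1.5y) | 28% / 28% | 13% | 99.5% | -0.48 / -0.48 |

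At large N the rule is met whenever dropout is associated with arm or baseline, whether or not the contrast is biased. At 12:4 it is met in 10.5% to 27% of trials under MCAR, arm-only MAR and the two MNAR settings. The 58% row has the tested covariate itself driving dropout. It reflects how strong that association is, not that the mechanism is MAR.

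**Step 3: the arm term alone at 12:4, with no donepezil dropout.**
- LR test, 6 of 12: 2 × {12 ln 0.5 − [6 ln(6/16) + 10 ln(10/16)]} = 2 × (−8.318 + 10.585) = 4.53, p = 0.033. For 5 of 12, p = 0.059.
- Fisher, 9 of 12: C(12,9)/C(16,9) = 220/11,440 = 0.019. For 8 of 12: 2 × 495/12,870 = 0.077.

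So 6 (LR) or 9 (Fisher) of 12 phenserine participants must drop out before arm is significant. At 23.6% versus 17.1% dropout this happens in 3.3% (LR) or 0.4% (Fisher) of trials.

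**The case against.** A reader might infer that the rule points the wrong way, because it is rarely met under harmless MCAR and nearly always met under biasing MNAR when N is large. That comparison omits arm-only dropout, which is also harmless and also meets the rule in 100% of large-sample runs. The accurate statement is that the rule does not discriminate. For the same reason, arm-related dropout is not in itself a source of bias. If dropout depends on arm alone, it is MAR given treatment, and treatment is in both the protocol and SAP models.

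A reader might also infer that biased dropout would be certified as ignorable. The text says only that MAR would be supported, promises sensitivity analyses in the next sentence and ties no analysis to the result. At 12:4 the rule was met in only 13% to 27% of the simulated MNAR trials.

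Nor is intolerance the same as missing data here. Protocol 6.6 has participants continue at a reduced dose, and section 7 keeps withdrawn participants under assessment. By design, only those who withdraw consent have no further assessments. Section 10.1 replaces very early dropouts. Actual missingness may be well below the simulated rates.

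The bias sizes are assumed too. With a steeper mechanism (logit slope 2 per SD) and a raw single-visit difference, the bias is about -0.4 SD. Slopes of 0.5 to 1 give -0.11 to -0.22. Keeping slope 2 but using three earlier visits in a likelihood-based estimate gives -0.27, -0.19 or -0.10 at within-person correlations of 0.5, 0.7 or 0.85.

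All of this stands and limits the consequence. It does not make the inference valid. The SAP's silence does not withdraw the protocol sentence, and the SAP also omits the one safeguard that the protocol offers.

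**Conclusion.** The stated inference is wrong and should be removed. That conclusion rests on the argument in Step 1 and needs no assumed dropout rate. The simulations only illustrate it: 100% versus 100% at large N under arm-only MAR (bias 0.00 SD) and MNAR (bias -0.32 SD), and 10.5% to 27% at the planned size under MCAR, arm-only MAR and MNAR. The bias figures are not forecasts for this trial.

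The practical weight is moderate. The study is exploratory, p-values are descriptive and the rule controls nothing. What remains is an invalid claim in the protocol, a sensitivity analysis without a method and with the wrong target, and a SAP that neither revokes the first nor carries forward the second. One further point bears on the claim. Dropout explained by a covariate is ignorable only if the analysis conditions on that covariate. SAP 7.2 has treatment, visit and their interaction but no baseline term, whereas the Protocol 10.3 model adjusts for the baseline biomarker. A dropout model that is significant because of baseline would therefore not reassure about the SAP model.

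**What to change.** 1. In Protocol 10.3, delete the sentence that sets out to demonstrate MAR and the sentence that reads a significant model as support for it. The dropout regression may stay only as a description of who dropped out.
2. State MAR as an untestable working assumption of the mixed model.
3. Report count, timing and reason for missing exosome data by arm. SAP 3.3 already gives reasons for withdrawal. The addition matters because section 7 counts withdrawn participants as dropouts although their assessments continue, so dropout and missing biomarker data are not the same.
4. Aim the promised sensitivity analysis at the treatment contrast. For example, shift the missing ln-biomarker values by a fixed delta from -1 to +1 SD in steps, in each arm separately and then in both, and show how the estimate and its 95% CI move. Both directions are needed because the panels mix markers such as BAX and Bcl-2, or TNF-α and IL-10. Read the result by the change in estimate and interval, not by loss of significance, in line with SAP 2.3.2.
5. Name this in SAP section 6 as a sensitivity-only exception to the no-imputation rule, and reconcile Protocol 10.3 with SAP section 6.

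Cost: wording in both documents and a short extra program. The report can no longer claim that MAR was supported.

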10.3.1. General Considerations

The statistical analysis plan for this study is designed to assess the efficacy, safety, and pharmacokinetic properties of phenserine compared to donepezil in participants with early or mild Alzheimer's Disease (AD). Analyses will be conducted on a modified intent-to-treat (mITT) population, which includes all randomized participants who receive at least one dose of study medication and have at least one post-baseline assessment. All statistical tests will be two-sided, with a significance level set at 0.05.

10.3.2. Primary Endpoints Analysis

10.3.3. Definition of endpoint(s)

The primary endpoint of this study is the change from baseline in exosome biomarkers, including markers of pre-programmed cell death. These biomarkers plasma are critical indicators of neurodegenerative processes in AD.

10.3.4. Main Analytical Approach

The primary analysis will compare the change in exosome biomarker levels between the phenserine and donepezil treatment groups. The model will adjust for baseline biomarker levels, treatment group, and any other relevant covariates.

10.3.5. Secondary Endpoints Analysis

The secondary endpoints include safety and tolerability, cognitive performance, and pharmacokinetic parameters. Safety and tolerability will be assessed by comparing the incidence and severity of adverse events (AEs) between treatment groups.

10.3.6. Exploratory Endpoints Analysis

Exploratory endpoints focus on changes in blood and CSF biomarkers and their relationship with clinical outcomes.

10.3.7. Safety Analyses

Safety analysis will involve descriptive analysis comparing frequencies between the two treatment groups with frequency AEs and SAEs.

10.4. Sample Size Determination

A sample size of 16 participants for this initial dose-range finding study of phenserine is expected to provide adequate data to inform dose selection and study design for a follow-on Phase 2 trial in a larger sample of participants with early or mild AD.

The primary outcome is the difference in key protein levels measured in neuronally derived exosomes between treatment groups. Previous studies (Goetzl et al.) (30,31) have shown between-group differences of 4.9 standard deviations (SD) in similar measures. Conservatively, this study assumes an effect size of half that magnitude (2.45 SD). Based on this assumption, a sample size of 16+4 4 participants would be required to achieve 80% power to detect a statistically significant difference ($p < 0.05$) between treatment groups.

11. Supporting Documentation and Operational Considerations

11.1. Appendix 1: Regulatory, Ethical, and Study Oversight Considerations

11.1.1. Regulatory and Ethical Considerations

Regulatory compliance

Before data collection commences, the Coordinating Investigator will ensure that appropriate research ethics committee (REC) approvals are in place.

If any amendments are required, the Coordinating Investigator will ensure that information is submitted to the REC in order for that body to issue approval for the amendment. Amendments will only be implemented once approval has been granted.

The Coordinating Investigator will further ensure that this study is conducted in accordance with International Council for Harmonisation (ICH) guidelines, or with the laws and regulations of the country in which the research is conducted, whichever affords the greater protection to the study patient.

The Investigators will also ensure adherence to the basic principles of Good Clinical Practice (GCP).

Regulatory and Ethical Considerations

- This study will be conducted in accordance with the protocol and with the following:
- Consensus ethical principles derived from international guidelines including the Declaration of Helsinki and Council for International Organizations of Medical Sciences (CIOMS) international ethical guidelines
- Applicable ICH Good Clinical Practice (GCP) guidelines
- Applicable laws and regulations
- The protocol, protocol amendments, ICF, investigator's brochure, Investigational Directions for Use (IDFU), and other relevant documents (eg, advertisements) must be submitted to an IRB/IEC by the investigator and reviewed and approved by the IRB/IEC before the study is initiated.

Any amendments to the protocol will require IRB/IEC approval before implementation of changes made to the study design, except for changes necessary to eliminate an immediate hazard to study participants.

- Protocols and any substantial amendments to the protocol will require health authority approval prior to initiation except for changes necessary to eliminate an immediate hazard to study participants.
- The investigator will be responsible for the following, as applicable:
 - Providing written summaries of the status of the study to the IRB/IEC annually or more frequently in accordance with the requirements, policies, and procedures established by the IRB/IEC
 - Notifying the IRB/IEC of SAEs or other significant safety findings as required by IRB/IEC procedures.

- Providing oversight of the conduct of the study at the site and adherence to requirements of 21 CFR, ICH guidelines, the IRB/IEC, European regulation 536/2014 for clinical studies, European Medical Device Regulation 2017/745 for clinical device research, and all other applicable local regulations

This clinical trial will be conducted in accordance with the Clinical Trial Regulation (EU 536/2014), ensuring that all processes and procedures comply with the regulatory requirements set forth by the European Union. The study will adhere to Good Clinical Practice (GCP) guidelines, national laws, and ethical standards to safeguard participant rights, safety, and well-being throughout the trial.

Financial Disclosure

Investigators and subinvestigators will provide the sponsor with sufficient, accurate financial information as requested to allow the sponsor to submit complete and accurate financial certification or disclosure statements to the appropriate regulatory authorities. Investigators are responsible for providing information on financial interests during the course of the study and for 1 year after completion of the study.

Participant Confidentiality

- The investigator or the investigator's representative will explain the nature of the study, including the risks and benefits, to the potential participant and answer all questions regarding the study.
- To prevent compromises to voluntary informed consent, written consent must be obtained from a physician with an independent relationship to the potential participant. This means that if the patient's treating physician is study investigator, he/she cannot carry out the consent procedure with her/his patient.
- Potential participants must be informed that their participation is voluntary. They will be required to sign a statement of informed consent that meets the requirements of local regulations, ICH guidelines, privacy, and data protection requirements, where applicable, and the IRB/IEC or study center.
- The medical record must include a statement that written informed consent was obtained before the participant was enrolled in the study and the date the written consent was obtained. The authorized person obtaining the informed consent must also sign the ICF.
- Participants must be reconsented to the most current version of the ICF(s) during their participation in the study.

Participant Confidentiality

Personal data will be collected on the consent form and as a log of participants. Paper records will be securely stored in a locked cabinet in a secure room. Electronic records will be password protected on institutional computers. Personal records will be kept separately from research records.

Research assessments will be completed using electronic and paper schedules, using only study numbers as identifiers. Data and schedules will be securely stored and electronic data will be password protected. All data will be stored using a linked anonymized system so that no personal identifiers are present on the schedules or databases including the collected study data.

Any personal data stored on institutional computers will be subject to appropriate access controls ensuring that access to confidential research information is password protected and restricted to those who need access.

All procedures will be in full compliance with the GDPR.

Data Protection

The documentation of the clinical trial data in adherence to the GCP-guidelines and the trial protocol is the responsibility of the investigator. All essential documents will be kept in the Investigator Site File (ISF), which will be stored at the trial site in accordance with ICH GCP. Original data (source documents) remain in hospital medical records and information in the eCRF must be traceable and consistent with the original data. Source documents are e.g., laboratory results, measurements of clinical scales, vital sign measurements, and questionnaires. No information in source documents about the identity of the patients will be disclosed. Data collected in this clinical trial (see study procedures and trial flow chart) except data for exploratory analysis must be entered in an eCRF which has to be completed by the investigator or authorized trial personnel and signed by the investigator. This also applies for those patients who do not complete the clinical trial. If a patient withdraws from the clinical trial, the reason must be recorded in the eCRF. The principal investigator holds the responsibility for ensuring the accuracy, completeness, and punctuality of all data submitted to the sponsor in the eCRFs and in all mandatory reports.

After database lock, the principal investigator will receive data on an electronic device that includes the investigational site data for archiving in the Investigator Site File (ISF). Data are processed by data management by the study statistician and his team with the support of a study database (eCRF) according to the SOPs. The evaluation of the data takes place by programmed validity and consistency checks. The description of the electronic data capture (EDC) system is detailed in Appendix 5.

Monitoring activities are performed, by NORCRIN, to ensure that the trial is conducted in accordance with the trial protocol, the principles of GCP, and local legislation. A monitoring manual will be applied, describing the scope of the monitoring activities in detail. A monitoring visit report is prepared for each visit describing the progress of the clinical trial and all identified problems. If a pandemic situation will not allow an on-site monitoring, remote monitoring or monitoring by phone is possible if data protection aspects are considered.

Participants will be assigned a unique identifier by the sponsor. Any participant records or datasets that are transferred to the sponsor will contain the identifier only; participant names or any information which would make the participant identifiable will not be transferred.

The participant must be informed that their personal study-related data will be used by the sponsor in accordance with local data protection law. The level of disclosure must also be explained to the

participant who will be required to give consent for their data to be used as described in the informed consent.

The participant must be informed that their medical records may be examined by Clinical Quality Assurance auditors or other authorized personnel appointed by the sponsor, by appropriate IRB/IEC members, and by inspectors from regulatory authorities.

The contract between sponsor and study sites specifies responsibilities of the parties related data protection, including handling of data security breaches and respective communication and cooperation of the parties.

Information technology systems used to collect, process, and store study-related data are secured by technical and organizational security measures designed to protect such data against accidental or unlawful loss, alteration, or unauthorized disclosure or access.

Trial management

[name] is the Chief Investigator and will have academic oversight of the trial and be responsible for reporting to the funder. The Coordinating Investigator for the PATH-1 RCT is [name], who will have overall responsibility for the conduct of the trial and interactions with the sponsor, regulator, and ethics committee, as appropriate and required during the course of the trial. [name] will be responsible for the analysis of exosomes, the primary outcome measure.

This trial will be managed by a Trial Management Group (TMG), which will include the Principal Investigators, the Trial Manager and a patient representative. The TMG will be co-chaired by the Chief Investigator and the Coordinating Investigator. The group will meet at three-month intervals and additionally as appropriate. The TMG will have direct oversight of and responsibility for the study. The remit of the TMG will also include overall progress of the trial and to monitor progress against milestones. Any discrepancy from milestones will be highlighted and a plan developed to address any difficulties. The day-to-day management of the trial will be conducted by the Trial Manager, who will report to the Coordinating Investigator on a regular basis. The Trial Manager will send a written report to the chairs of the TMG before each TMG meeting, detailing progress. Any non-urgent major decisions will be made by the TMG.

The Trial Steering Committee (TSC), , will meet twice over the course of the study (with additional meetings convened if requested by the Data and Safety Monitoring Board (DSMB) and will be responsible for oversight of trial governance and reporting to the sponsor.

A DSMB chaired by [name] (Geriatrician) will provide independent review of unblinded safety data collected during the study. All serious adverse events (SAEs) will be reviewed by the chair within 24 hours, and summary trial reports will be reviewed by the full committee every three months through its completion. The data will be prepared for these reviews by a separate team of unblinded data managers and statisticians who have no involvement in the day-to-day conduct of the study.

The committee will be governed by a charter and will make recommendations to stop, continue or modify the trial based on their ongoing review of the safety data. Emergency meetings will be convened on an ad hoc basis and as warranted by emergent study data.

The DSMB and TSC will monitor recruitment, ethical issues and safety and will have the ultimate responsibility for the continuation or discontinuation of the study.

Dissemination of Clinical Study Data

The clinical trial results will be uploaded in CTIS within 1 year after study end.

Data Quality Assurance

- All participant data relating to the study will be recorded on electronic CRFs unless transmitted to the sponsor or designee electronically (eg, laboratory data). The investigator is responsible for verifying that data entries are accurate and correct by physically or electronically signing the CRF.
- Guidance on completion of CRFs will be provided in a SOP.
- The investigator must permit study-related monitoring, audits, IRB/IEC review, and regulatory agency inspections and provide direct access to source documents.
- Monitoring details describing strategy, including definition of study critical data items and processes (e.g., risk-based initiatives in operations and quality such as risk management and mitigation strategies and analytical risk-based monitoring), methods, responsibilities, and requirements, including handling of noncompliance issues and monitoring techniques (central, remote, or on-site monitoring) are provided in the monitoring plan.
- The sponsor is responsible for the data management of this study, including quality checking of the data.
- The sponsor assumes accountability for actions delegated to other individuals (eg, contract research organizations).
- The investigator shall archive the content of the clinical trial master file for at least 25 years after the end of the clinical trial.
- Medical files of subjects shall be archived in accordance with national law.
- No records may be destroyed during the retention period without the written approval of the sponsor. No records may be transferred to another location or party without written notification to the sponsor.

Source Documents

- Source documents provide evidence for the existence of the participant and substantiate the integrity of the data collected. Source documents are filed at the investigator's site.
- Data reported on the CRF or entered in the eCRF that are transcribed from source documents must be consistent with the source documents or the discrepancies must be explained. The investigator may need to request previous medical records or transfer records, depending on the study. Also, current medical records must be available.
- Definition of what constitutes source data and its origin can be found in monitoring guidelines.

- The investigator must maintain accurate documentation (source data) that supports the information entered in the CRF.
- The sponsor or designee will perform monitoring to confirm that data entered into the CRF by authorized site personnel are accurate, complete, and verifiable from source documents; that the safety and rights of participants are being protected; and that the study is being conducted in accordance with the currently approved protocol and any other study agreements, ICH GCP, and all applicable regulatory requirements.

Protocol compliance

Protocol deviations will be reported to the Trial Manager, Coordinating Investigator and Sponsor immediately. An Exception Report will be prepared by the Trial Manager, covering a summary and chronology of events, an assessment of risk and details of the corrective actions to be taken. The Coordinating Investigator will monitor all deviations, ensure that the necessary corrective actions are taken, and identify and address through preventive action any instances where a deviation recurs.

Study and Site Start and Closure**First Act of Recruitment**

The study start date is the date on which the clinical study will be open for recruitment of participants.

The first act of recruitment is the first site open and will be the study start date.

Study/Site Termination

The sponsor or designee reserves the right to close the study site or terminate the study at any time for any reason at the sole discretion of the sponsor. Study sites will be closed upon study completion. A study site is considered closed when all required documents and study supplies have been collected and a study-site closure visit has been performed.

The investigator may initiate study-site closure at any time, provided there is reasonable cause and sufficient notice is given in advance of the intended termination.

Reasons for the early closure of a study site by the sponsor or investigator may include but are not limited to:

For study termination:

- Discontinuation of further study intervention development

For site termination:

- Failure of the investigator to comply with the protocol, the requirements of the IRB/IEC or local health authorities, the sponsor's procedures, or GCP guidelines
- Inadequate or no recruitment (evaluated after a reasonable amount of time) of participants by the investigator
- Total number of participants included earlier than expected
- Recruitment rate is considered too low

If the study is prematurely terminated or suspended, the sponsor shall promptly inform the investigators, the IECs/IRBs, the regulatory authorities, and any contract research organization(s) used in the study of the reason for termination or suspension, as specified by the applicable

regulatory requirements. The investigator shall promptly inform the participant and should assure appropriate participant therapy and/or follow-up.

Publication Policy

- The results of this study may be published or presented at scientific meetings. If this is foreseen, the investigator agrees to submit all manuscripts or abstracts to the sponsor before submission. This allows the sponsor to protect proprietary information and to provide comments.
- The sponsor will comply with the requirements for publication of study results. In accordance with standard editorial and ethical practice, the sponsor will generally support publication of multicenter studies only in their entirety and not as individual site data. In this case, a coordinating investigator will be designated by mutual agreement.
- Authorship will be determined by mutual agreement and in line with International Committee of Medical Journal Editors authorship requirements.

Role of Trial Sponsor

Stavanger University Hospital is the sponsor with legal responsibility for the research integrity of the study. This role will be delegated to the Coordinating Investigator.

The sponsor will ensure that the research team has access to resources and support to deliver the research as proposed and that responsibilities for management, monitoring and reporting of the research are in place prior to the study commencing. The sponsor will ensure that there is agreement on recording, reporting and reviewing significant developments as the research proceeds and approve any modifications to design, obtaining requisite regulatory authority.

The sponsor will assume responsibility for operating the management and monitoring systems of the research.

